9.2.2 Efficacy Analyses in the Withdrawal Period

The distribution of event-free survival defined in Section 3.1 will be estimated using Kaplan-Meier (KM) method. Subjects who did not have flare event will be censored at the last available flare assessment visit at or prior to Week 152 visit. If a subject discontinued prior to flare or Week 152 visit, the data will be censored at the date of last flare assessment. The KM estimator for median survival time for the flare-free rate during the Withdrawal period will be provided. The corresponding 95% CI will be derived based on Greenwood's formula for variance derivation and the log-log transformation applied on the survival function. The KM plot will be provided.

Binary and continuous endpoints defined in Section 3.1 and Section 3.2 will be analyzed at scheduled time points during the Withdrawal Period.

For binary endpoints, NRI will be used for missing data handling (see Section 9.2.1.2). Descriptive statistics, including point estimate and 95% CI by normal approximation, will be provided.

For continuous endpoints, MMRM model (as described in Section 9.2.1.3) will be used based on observed data. Mean estimates with associated 95% CI will be provided. In addition, descriptive statistics based on observed data will be provided, including the number of observations, mean, and standard deviation.

Plots of efficacy endpoints by visit during the Withdrawal Period will be provided for selected endpoints.

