4 INVESTIGATIONAL PLAN

4.1 Overall Study Design and Plan

This is a global Phase 3, multicenter, protocol with a common screening platform and other operational elements of study conduct. The master protocol includes 2 independent studies for subjects with active axSpA including bDMARD-IR AS (Phase 3 study, Study 1) and nr-axSpA (Phase 3 study, Study 2).

Although this protocol includes a common screening process and other operational elements of study conduct for Study 1 and Study 2, randomization and data collection will be conducted for each study independently. The analyses and reporting for the 2 studies will also be separate. Each study represents a standalone study which may be reported individually for regulatory purposes.

Study 1 (bDMARD-IR AS) is comprised of a 35-day Screening Period; a 14-week randomized, double-blind, parallel-group, placebo-controlled period (the Double-Blind Period); a 90-week open-label, long-term extension period (the Open-Label Extension Period); and a 30-day Follow-Up Visit (F/U Visit).

Study 2 (nr-axSpA) is comprised of a 35-day Screening Period; a 52-week randomized, double-blind, parallel-group, placebo-controlled period (the Double-Blind Period); a 52-week open-label, long-term extension period (the Open-Label Extension Period); and a 30-day F/U Visit.

For both studies, a 30-day F/U phone call may be performed in place of a visit to determine the status of any ongoing AEs/SAEs or the occurrence of any new AEs/SAEs is required; these subjects will be considered as having completed the study.

Up to and including Week 14 of each study, a ± 3 day window is permitted around scheduled study visits. After Week 14 of each study, a ± 7 day window is permitted around scheduled study visits. If a subject has an out of window visit, the next visit should occur as originally scheduled based on the first date of study drug administration (Baseline Visit).

In the Double-Blind Period, subjects will be randomized in a 1:1 ratio to 1 of 2 treatment groups:

Study 1 (bDMARD-IR AS):

- Group 1: upadacitinib 15 mg QD (N = 193)
- Group 2: placebo QD (N = 193)

Study 2 (nr-axSpA):

- Group 1: upadacitinib 15 mg QD (N = 152)
- Group 2: placebo QD (N = 152)

Subjects in the placebo group will be switched to upadacitinib 15 mg QD at Week 14 in the Open-Label Extension Period for Study 1 (bDMARD-IR AS) and to upadacitinib 15 mg QD at Week 52 in the Open-Label Extension Period for Study 2 (nr-axSpA).

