3.0 Endpoints for Remission-Withdrawal Study

3.1 Endpoints for Withdrawal Period

During the Withdrawal Period, the time-to-flare endpoint is defined as follows:

- Flare event criterion is defined as ASDAS (CRP) score > 2.1 at two consecutive visits, which are at least 2 weeks apart, or ASDAS (CRP) score > 3.5 at one visit
- Time-to-flare is defined as the number of days between the first day of treatment withdrawal and the day on which the criterion is met.

Additional endpoints during the Withdrawal Period include the following measurements assessed at scheduled time points in the Withdrawal Period:

Binary variables:

- Assessment of SpondyloArthritis international Society (ASAS) 20 response*;
- ASAS40 response*

- Bath Ankylosing Spondylitis Disease Activity Index (BASDAI) 50 response* ;
- ASAS Partial Remission (PR);
- Inactive Disease based on ASDAS(CRP) (ASDAS score < 1.3)
- Low Disease Activity based on ASDAS(CRP) (ASDAS score < 2.1);
- Major Improvement based on ASDAS(CRP) (a change from Original Baseline of ≤ 2.0);
- Clinically Important Improvement based on ASDAS(CRP) (a change from Original Baseline of ≤ 1.1);

* *Relative to Original Baseline.*

Change from Original Baseline in:

- ASDAS(CRP) and components;
- BASDAI and BASDAI components including mean of question 5 and 6 of the BASDAI (Score 0 - 10);
- Bath Ankylosing Spondylitis Functional Index (BASFI) (Score 0 - 10);
- Linear Bath Ankylosing Spondylitis Metrology Index (BASMI_{lin});
- Maastricht Ankylosing Spondylitis Enthesitis Score (MASES) for subjects with baseline enthesitis (MASES > 0);
- Patient's Assessment of Total Back Pain NRS score 0 - 10;
- Patient's Assessment of Nocturnal Back Pain NRS score 0 - 10;
- Patient's Global Assessment of Pain NRS score 0 - 10;
- Physician's Global Assessment of Disease Activity (PGA) Numeric Rating Scale (NRS) score 0 - 10;
- Patient's Global Assessment of Disease Activity (PtGA) NRS score 0 - 10;
- Tender joint count (TJC68) and swollen joint count (SJC66);
- ASAS Health Index (HI).

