9.2.1.1 Time-to-Flare

After handling of intercurrent events, for subjects without observed flare event, time-to-flare will be censored at the last available flare assessment at or prior to Week 152 visit.

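### Censoring flare-free completers at their own Week 152 date pulls down the end of the time-to-flare Kaplan-Meier curve and can show a median that was not reached

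*SAP*

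**What the plan says.** SAP 3.1 sets the clock: "Time-to-flare is defined as the number of days between the first day of treatment withdrawal and the day on which the criterion is met". SAP 9.2.1.1 says that without an observed flare "time-to-flare will be censored at the last available flare assessment at or prior to Week 152 visit", and SAP 9.2.2 repeats the rule: "Subjects who did not have flare event will be censored at the last available flare assessment visit at or prior to Week 152 visit". For subjects who discontinue, SAP 9.2.2 says "the data will be censored at the date of last flare assessment".

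Protocol 4.1 governs visit timing: "After Week 14 of each study, a ± 7 day window is permitted around scheduled study visits". Visits are anchored on the Baseline date, so an early or late Week 104 visit does not move the Week 152 target.

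A flare can be met for the first time at Week 152. SAP 3.1 reads: "Flare event criterion is defined as ASDAS (CRP) score > 2.1 at two consecutive visits, which are at least 2 weeks apart"; a single score above 3.5 also counts. Week 140 plus Week 152, or Week 152 alone, can therefore supply the event.

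SAP 9.2.2 reports the Kaplan-Meier median and a plot. Protocol 7.3 also promises the flare-free rate with a 95% CI. Neither document assigns nominal visit times, sets a common censoring day, names an interval-censored estimator, or fixes a landmark at which the rate is read.

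**The concern.** Flare is observed only at assessments. Subjects who reach Week 152 without flare have all had the same last look, and the calendar spread of that look says nothing about their risk. On actual dates, however, a completer seen early in the window leaves the risk set before a flare found at the same visit a few days later. The late flare is then divided by the few subjects who also attended late.

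This does not happen at Weeks 110 to 140, because flare-free subjects remain at risk after those visits. It is confined to the last visit. The open-label extension schedule (Protocol Appendix F) collects neither the patient-reported scores nor hsCRP, so no later flare assessment keeps completers in the risk set.

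At stake are the end of the plotted curve, any flare-free rate read there, and the planned median. The Greenwood interval uses the same shrunken risk sets, so it does not correct the bias.

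**Working it through.** The documents give no number entering withdrawal, flare rate or median, so there is no planned figure to reproduce.

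**Inputs from the documents.** Visits fall at Weeks 110, 116, 122, 128, 140 and 152 (Protocol Appendix D). Week 152 is (152 − 104) × 7 = 336 days after Week 104. The window is ±7 days, which gives 15 possible days per visit. Taking withdrawal to start at the Week 104 visit, time since withdrawal at Week 152 runs from 336 − 14 = 322 to 336 + 14 = 350 days.

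**Assumed inputs.** Number at risk, flare probability at each visit, dropout, and attendance spread within the window.

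**Step 1: the last-visit step in closed form.** Spread the subjects at risk evenly over the 15 window days, each flaring at that visit with probability p. With k days left, counting the current one, the flares are a fraction p/k of those still at risk. The true factor is 1 − p. The actual-date factor is the product over k = 1 to 15 of (1 − p/k). Its k = 1 term alone equals the true factor; the other 14 terms are artefact.

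| p | True factor | Actual-date factor |
|---|---|---|
| 3% | 0.97 | 0.905 |
| 5% | 0.95 | 0.845 |
| 10% | 0.90 | 0.712 |
| 15% | 0.85 | 0.596 |

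**Step 2: two whole-period patterns.**
- Later flares, 3/8/9/8/10/10% at the six visits. Before Week 152: 0.97 × 0.92 × 0.91 × 0.92 × 0.90 = 0.672. True end: 0.672 × 0.90 = 0.605. Actual-date end: 0.672 × 0.712 = 0.479.
- Front-loaded flares, 10/12/10/6/5/3%. Before Week 152: 0.90 × 0.88 × 0.90 × 0.94 × 0.95 = 0.637. True end: 0.637 × 0.97 = 0.617. Actual-date end: 0.637 × 0.905 = 0.576.

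With the Week 152 window alone, the bias is therefore about −13 and −4 points.

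**Step 3: simulation with both windows and about 2% dropout per visit.**
- Later flares: the actual-date curve ends at 0.48, 0.45–0.47 and 0.43–0.44 for N = 30, 60 and 100. Nominal weeks give 0.60–0.61. Among runs where the nominal-week estimate exceeds 0.50, the actual-date curve still falls to 0.50 or below in 36% to 56%.
- Front-loaded flares: the end bias is about −4.5 to −6 points, with a false median in 11% to 19% of all runs.
- Read at day 336, the later-flare curve gives about 0.62 against 0.605, an error of 1.5 points upward.

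**Step 4: other flare-free rates.** These runs used n = 50 or 100, 5% dropout, constant or front-loaded hazard, and uniform or clustered attendance.

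| True flare-free rate | Flaring at last visit | Mean end of actual-date curve | False median |
|---|---|---|---|
| 0.60 | 7–12% | 0.40–0.52 | 28–66% |
| 0.70 | 5–9% | 0.53–0.63 | 9–32% |
| 0.80 | 3–5% | 0.66–0.75 | 2–13% |

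**Step 5: tied dates.** Sixty subjects cannot have distinct dates in 15 or 29 days, and ties soften the effect. With 60 at risk and 5 flares the true step is 55/60 = 0.917. Allowing ties, the actual-date step averages 0.75 with one window and about 0.69–0.70 with both.

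**The case against.** The strongest reply is that the reading is inferred. For completers, SAP 9.2.2 speaks of an assessment visit; the word date appears only for discontinuations, and the SAP never says actual visit date. That is fair. But an endpoint counted in days to the day of the criterion points to actual dates, and nothing in the text directs the programmer to nominal weeks.

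Second, the analysis is descriptive with no testing (SAP 9.1 and 13.0), and the protocol lists time to flare as an additional endpoint. Both stand. A reader might infer that type I error, or a primary conclusion of the trial, is compromised. The documents do not support that, because no hypothesis is tested in this period.

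Third, the damage is confined to the last visit. A reader might infer that the whole curve is distorted or that any reported median is false. Neither follows. Earlier steps are essentially right, day 336 is close, and a median reached before the window is unaffected.

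Fourth, ASDAS low disease activity and inactive disease are reported by scheduled visit with non-responder imputation and do not carry this artefact. This is a partial check only: they are not the flare endpoint.

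Fifth, the sizes depend on assumptions. Unscheduled visits include an ASDAS calculation, so some flares could be confirmed before Week 152, which the simulations omit. This could reduce the size. The downward direction at the end of the curve remains when flares first met at Week 152 follow the departure of flare-free completers.

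**Conclusion.** The concern holds on the natural reading of the SAP. Following the text gives a Kaplan-Meier curve whose end is biased downward whenever flares are first met at Week 152 after flare-free completers have been censored. With a true flare-free rate of about 0.60 to 0.62, the bias is roughly −5 points when 3% flare at the last visit and up to about −17 points when 10% do. A median is shown in error in about 15% of runs under the first pattern and up to about 55% under the second. False medians become rarer as the true flare-free rate rises.

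These sizes rest on assumed N, hazards, dropout and attendance spread, none of which the documents give. The harm is a misleading curve tail, flare-free rate or median in a single-arm descriptive analysis. It is worth correcting because in such an analysis the estimate is the result.

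**What to change.** In SAP 3.1, 9.2.1.1 and 9.2.2, run the Kaplan-Meier analysis on nominal visit weeks. All Week 152 flares and censorings then tie at day 336, with events counted first. Report the Week 152 flare-free rate and its 95% CI from that curve. State how flares at unscheduled visits, and re-treatment counted as flare under SAP 8.0, map to a visit week.

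Alternatively, keep actual days but censor every flare-free completer at one common day on the withdrawal clock, at or after the latest possible Week 152 flare. That is day 350 if windows are respected, and later if a Week 152 flare is found out of window. In simulation with the later-flare pattern this ended at 0.60–0.61 against a truth of 0.605.

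Three nearby choices do not work under that pattern:
- A common day 343 leaves later flares with no completers in the risk set; the curve ended at 0.39 (N = 60) and 0.29 (N = 100).
- Each subject's own window end still varies with the Week 104 date; it ended at 0.57.
- Truncating at the first window day (329) leaves out most Week 152 flares; it read 0.66.

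The cost is SAP wording and one date derivation, with no new data. The small downside of nominal weeks is that flare times are rounded to the visit week. If an unscheduled flare is moved to the next scheduled visit, the delay can approach 12 weeks late in the period.

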9.3 Re-Treatment Period Efficacy Analysis

9.3.1 Handling of Missing Data

Missing data will be handled as described below for the Re-treatment Period efficacy analysis.

9.3.1.1 Binary Endpoints

All reported data will be used with no missing data imputation.

9.3.1.2 Continuous Endpoints

Mixed-Effect Model Repeat Measurement (MMRM) analysis based on all observed data will be conducted with categorical fixed effect of visit and Re-treatment Baseline as the continuous fixed covariate. For summary in the overall subjects, an additional fixed effect of parent study (Study 1 or Study 2) will be considered. An unstructured variance covariance matrix will be used.

9.3.2 Efficacy Analyses in the Re-Treatment Period

Binary and continuous endpoints defined in Section 3.2 will be analyzed at scheduled time points during the Re-treatment Period.

For binary endpoints within the Re-treatment Period, descriptive statistics based on all observed data will be provided (see Section 9.3.1.1). Descriptive statistics include the point estimate and 95% CI by normal approximation.

For continuous endpoints within the Re-treatment Period, MMRM method (as described in Section 9.3.1.2) will be used based on all observed data. Mean estimates with 95% confidence intervals will be provided. In addition, descriptive statistics will be provided, including the number of observations, mean, and standard deviation.

Plots of efficacy endpoints by visit during the Re-treatment Period will be provided for selected endpoints.

10.0 Safety Analyses

10.1 General Considerations

Safety data will be summarized for the safety populations defined in Section 4.0.

The safety analyses will include reporting of adverse events (AEs), adverse events of special interest (AESI), laboratory, and vital sign measurements. Exposure-adjusted event rate (EAER) over 100 patient-years for subjects with treatment-emergent adverse events (TEAEs) will be provided to adjust for potentially different follow-up time between subjects. For the purpose of event rate calculation, the numerator will be the total number of AEs reported for the event (i.e., a subject can contribute more than one event to the numerator) and the denominator will be the total exposure time among subjects. The number of AEs reported (numerator), the total number of years of exposure (denominator calculated as total number of days of exposure for all treated subjects divided by 365.25), and the exposure-adjusted AE event rate per 100 patient-years calculated as $(\text{numerator} / \text{denominator}) \cdot 100$ will be presented.

In addition, exposure-adjusted incidence rate (EAIR) will be provided for AE Overview and Adverse Events of Special Interest (AESI) as deemed appropriate for long-term analysis. For the purpose of incidence rate calculation, the numerator will be the number

of subjects with AE reported for the event (i.e., a subject can contribute at most once to the numerator) and the denominator will be the total exposure time among subjects in the treatment group and at risk of an initial occurrence of the event, i.e., for subjects with no event, it is the total exposure time under the treatment group; for subjects with an event, it is the exposure time to the first event. The numerator, denominator (calculated as total number of days exposed to study drug for all treated subjects divided by 365.25), and the exposure-adjusted incidence rate per 100 patient-years calculated as $([\text{numerator}/\text{denominator}]) \cdot 100$ will be presented for each treatment group.

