2.2 Study Design Overview

Figure 1 shows the design of Study M19-944. Remission-Withdrawal Period is illustrated in the right portion.

Figure 1. Study Schematic

AS ankylosing spondylitis; ASAS Assessment of Spondyloarthritis International Society; bDMARD IR biologic disease modifying antirheumatic drug inadequate responder; EMA European Medicines Agency; FDA Food and Drug Administration; MRI magnetic resonance imaging; nr axSpA non radiographic axial spondyloarthritis; QD once daily; SI sacroiliac; UPA upadacitinib

Subjects in Study M19-944 from both Study 1 (AS bDMARD-IR) and Study 2 (nr-axSpA) who reach Week 104 on study drug (upadacitinib 15 mg QD) will be assessed whether they are in remission, with an ASDAS (CRP) < 1.3 at Week 104 and an ASDAS (CRP) < 2.1 at Week 88.

Subjects in remission at Week 104 will be eligible for the Remission-Withdrawal Period. Subjects will be followed without study drug treatment and assessed for disease flare through Week 152. Flare is defined as an ASDAS (CRP) \geq 2.1 at 2 consecutive visits (based on observed records), which are at least 2 weeks apart, or an ASDAS (CRP) > 3.5 at one visit. Subjects who flare will receive open-label re-treatment upadacitinib

15 mg QD from the time of flare for 24 weeks (re-treatment) or longer per local country requirements. Subjects who do not flare will be followed without upadacitinib treatment until Week 152 at which point they will have the option to receive open label upadacitinib for the predefined time period, if Week 152 is before the end of the Open-Label Extension Period for their respective country. If Week 152 is after the end of the Open-Label Extension Period, the subject will complete the study at Week 152.

Efficacy analyses will be performed to characterize subject response to treatment withdrawal up to 48 weeks and response to upadacitinib re-treatment for 24 weeks respectively. Safety analyses will be performed to assess safety of reinitiated upadacitinib 15 mg QD after treatment withdrawal, including re-treatment after flare and treatment during Open-Label Extension Period after withdrawal.

An additional safety analysis will be performed to assess the totality of upadacitinib safety in the M19-944 study.

For the purposes of subject disposition and efficacy analysis, the duration of withdrawal from treatment is defined as the Withdrawal Period. The 24 weeks of exposure to treatment after flare is defined as the Re-treatment Period.

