4.0 Analysis Populations

The Analysis Populations are defined in [Table 1](#) and [Table 2](#) below.

[figure not shown]
Table 1. Analysis Population for Efficacy Analyses

Analyses Population	Definition	Analyses Group
Withdrawal Analysis Set (WAS)	All subjects who entered the Remission-Withdrawal Period	Off Upadacitinib Treatment
Re-treatment Analysis Set (RAS)	All subjects who entered the Remission-Withdrawal Period and received at least one dose of Upadacitinib re-treatment in the Remission-Withdrawal Period	Upadacitinib 15 mg Re-treatment in RW

Table 2. Analysis Population for Safety Analyses

[figure not shown]
Analyses Population	Definition	Analyses Group	Data for Analyses
UPA reinitiation	All subjects who received at least one dose of reinitiated upadacitinib	Upadacitinib 15 mg	Safety data after reinitiation of upadacitinib (i.e., F+G+H as shown in Figure 2) will be included in safety analyses for summary of safety after reinitiating upadacitinib.
ALL UPA	All subjects who received at least one dose of upadacitinib in M19-944.	Any Upadacitinib 15 mg	Safety data under upadacitinib exposure in M19-944 (i.e., A+C+E+F+G+H in Figure 3) will be included in safety analyses for the totality of upadacitinib safety in M19-944.

Figure 2. Study Drug Exposure for Reinitiated Upadacitinib (UPA reinitiation)

Study 1 includes 14 week double blind placebo controlled period with 90 week open label period. Study 2 includes 52 week double blind placebo controlled period with 52 week open label period.

Figure 3. Study Drug Exposure for All Upadacitinib (ALL UPA)

Study 1 includes 14 week double blind placebo controlled period with 90 week open label period. Study 2 includes 52 week double blind placebo controlled period with 52 week open label period.

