10.2.1 Adverse Event Overview

An overview of TEAEs per 100 patient-years of study drug exposure will be presented for the following categories:

- Any TEAE
- Any TEAE related to study drug according to investigator assessment
- Any Severe TEAE
- Any Serious TEAE
- COVID-19 TEAE
- Any TEAE leading to discontinuation of study treatment
- Any TEAE Leading to Death
- All Deaths

The number of TEAEs reported, the total number of years of study drug exposure, and the TEAE rate per 100 patient-years will be presented. An overview of TEAE incidence rate per 100 patient-years of exposure will also be presented.

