10.2.4 Adverse Events of Special Interest

Adverse events of special interest will be summarized by SOC and PT and will be based on standardized or AbbVie-defined company MedDRA queries (SMQs or CMQs), or based on adjudication results. Adjudicated cardiovascular events will be summarized using the CAC adjudicated categories. Adverse events of special interest categories and detailed information about the search criteria are listed in [Table 4](#).

A summary of non-treatment-emergent malignancy events will also be presented.

Tabular listings of treatment-emergent adverse events of special interest will be provided.

An overview of AESIs per 100 patient-years of study exposure will be presented. The number of TEAEs reported, the total number of years of study drug exposure, and the TEAE rate per 100 patient-years will be presented. Additionally, an overview of AESIs Incidence rate per 100 patient-years of study drug exposure will be also presented.

Table 4. AESI for Upadacitinib with SMQs/CMQs/PTs Searches

AESI	Type of MedDRA Query	Broad or Narrow Search	SMQ/CMQ Search Criteria
Serious Infections	CMQ		"Infections" – Subset for SAEs
Opportunistic Infection excluding Tuberculosis and Herpes Zoster	CMQ		"Opportunistic Infection excluding Tuberculosis and Herpes Zoster"
Possible Malignancy	SMQ	Narrow	"Malignancies"
Malignancy	SMQ	Narrow	"Malignant tumours"
Non-Melanoma Skin Cancer (NMSC)	SMQ	Narrow	Skin Malignant tumours (Narrow SMQ) removing Melanoma CMQ
Malignancy excluding NMSC			"Malignant tumours" SMQ (Narrow) removing NMSC output
Lymphoma	SMQ	Broad	"Malignant Lymphomas"
Hepatic Disorder	SMQ	Narrow	"Drug Related Hepatic Disorders" comprehensive search
Adjudicated Gastrointestinal Perforations	Output from adjudication		
Anemia	CMQ		"Non-Hemolytic and Non-Aplastic Anemias"
Neutropenia	CMQ		"Hematological Toxicity – Neutropenia"
Lymphopenia	CMQ		"Hematological Toxicity – Lymphopenia"
Herpes Zoster	CMQ		"Herpes Zoster"
Renal Dysfunction	SMQ	Narrow	"Acute Renal Failure"
Active Tuberculosis	CMQ		"Active Tuberculosis"
Bone Fracture	CMQ		"Bone Fracture"
Serious Hypersensitivity Reaction	SMQ	Narrow	"Anaphylactic Reaction" (SMQ narrow) including "Angiodema" (SMQ Narrow) – subset to SAEs
Retinal Detachment	CMQ		"Retinal Detachment"
Acute Renal Failure	SMQ	Narrow	"Acute Renal Failure"

AESI	Type of MedDRA Query	Broad or Narrow Search	SMQ/CMQ Search Criteria
Adjudicated Cardiovascular Events	Output from CAC		
MACE*			
Cardiovascular Death			

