Appendix C. EAER and Normal Approximation Based 95% Confidence Interval

Assume the occurrence of TEAE of special interest follows a Poisson distribution and let λ denote the rate of occurrence of TEAE under the total exposure time for a treatment group. Let n be the number of AEs reported in Any upadacitinib 15 mg QD group. Let T be the total time exposed to study drug summed across all treated subjects in Any upadacitinib 15 mg QD group. Under the assumption that n follow Poisson distribution with parameters λT , the $\hat{\lambda} = n/T$.

Using normal approximation, the 95% confidence interval can be calculated by (Liu GF et al. 2006.¹⁰):

$$\hat{\lambda} \pm Z_{\alpha/2} \hat{\sigma}$$

Where $\hat{\sigma} = \sqrt{\frac{n}{T^2}}$

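### SAP 10.1 gives the exposure-adjusted incidence rate two different denominators; programming the second would understate incidence of common events

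*SAP*

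**What the plan says.** SAP Section 10.1 (Safety Analyses, General Considerations) specifies two rates.

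- **EAER.** All events are counted, including repeats within a subject. The denominator is total exposure: "denominator calculated as total number of days of exposure for all treated subjects divided by 365.25". Appendix C uses the same quantity: "Let T be the total time exposed to study drug summed across all treated subjects in Any upadacitinib 15 mg QD group".
- **EAIR.** Each subject is counted at most once. The denominator is first defined as exposure while at risk of a first occurrence. Subjects without the event contribute all their exposure, and "for subjects with an event, it is the exposure time to the first event". The next sentence, which lists what will be presented, describes the "denominator (calculated as total number of days exposed to study drug for all treated subjects divided by 365.25".

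The EAIR is planned for the adverse event overview and the adverse events of special interest (AESIs). The sections that call for it do not choose a denominator. Section 10.2.1 says "An overview of TEAE incidence rate per 100 patient-years of exposure will also be presented" and Section 10.2.4 says "an overview of AESIs Incidence rate per 100 patient-years of study drug exposure will be also presented". Appendix C covers only the EAER.

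**The concern.** The two EAIR sentences describe different quantities. The second nearly repeats the EAER wording of the preceding paragraph, so it was probably carried over. If it is programmed, a subject who enters the numerator once, at the first event, goes on adding patient-years afterwards. On-drug time at risk can never exceed total exposure, so the error can only lower the rate, which is the unhelpful direction for a safety summary.

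The shortfall also grows with length of exposure, whereas exposure adjustment is meant to remove differences in follow-up. The SAP reports two safety populations whose exposure will differ, ALL UPA and UPA reinitiation. The latter is wider than the 24-week re-treatment: Table 2 covers "Safety data after reinitiation of upadacitinib (i.e., F+G+H as shown in Figure 2"), and Section 2.2 describes it as "including re-treatment after flare and treatment during Open-Label Extension Period after withdrawal". The documents do not give the length of that extension exposure, so the contrast between the two populations cannot be sized.

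**Working it through.** The documents state no EAIR value, so there is no planned figure to reproduce. The check compares the two denominators.

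**1. Fixed example (all counts assumed).** Take 100 subjects with 728 days on drug each, of whom 60 have a first event at day 182 and stay on drug.

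- At risk: (40 × 728 + 60 × 182) / 365.25 = 40,040 / 365.25 = 109.6 patient-years (PY). EAIR = 100 × 60 / 109.6 = 54.7 per 100 PY.
- Total exposure: 100 × 728 / 365.25 = 199.3 PY. EAIR = 100 × 60 / 199.3 = 30.1 per 100 PY.
- Ratio: 109.6 / 199.3 = 0.55.
- If the 60 subjects stop drug at the event, total exposure is also 109.6 PY and both formulas give 54.7.

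**2. Planned main-study exposure.** Arm sizes and treatment durations come from the Protocol Synopsis. All subjects are assumed to complete Week 104.

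| Arm | n | Weeks on upadacitinib | Subject-weeks |
|---|---|---|---|
| Study 1, upadacitinib | 193 | 104 | 20,072 |
| Study 1, placebo then upadacitinib | 193 | 90 | 17,370 |
| Study 2, upadacitinib | 152 | 104 | 15,808 |
| Study 2, placebo then upadacitinib | 152 | 52 | 7,904 |
| Total | 690 | mean 88.6 | 61,154 |

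61,154 × 7 / 365.25 = 1,172 PY.

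**3. Formula.** Assume a constant first-event rate λ per PY and that subjects stay on drug after the event. Let arm i have n_i subjects with τ_i years of exposure. Expected first events are Σ n_i(1 − exp(−λτ_i)), and expected time at risk is that sum divided by λ. The at-risk formula returns λ. The total-exposure formula returns λ times

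ratio = Σ n_i(1 − exp(−λτ_i)) / (λ Σ n_i τ_i).

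For λ = 0.10, expected first events are 34.9 + 30.6 + 27.5 + 14.4 = 107.3 (unrounded terms). Time at risk is 107.3 / 0.10 = 1,073 PY. The reported rate is 100 × 107.3 / 1,172 = 9.2 instead of 10.

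| True rate per 100 PY (assumed) | Ratio | Reported with total exposure |
|---|---|---|
| 2 | 0.982 | 1.96 |
| 5 | 0.957 | 4.8 |
| 10 | 0.916 | 9.2 |
| 30 | 0.775 | 23.3 |
| 100 | 0.471 | 47 |

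Solving for the ratio, the understatement reaches 5% at a true rate of 5.8 per 100 PY, 10% at 12.0, 20% at 26.1 and 50% at 90.7.

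**4. Sensitivity to early discontinuation.** Protocol 7.7 allows for 10% dropout at Week 14. If 10% of each arm leaves then, exposure is 1,064 PY and the ratios at 10 and 100 per 100 PY are 0.917 and 0.475. With discontinuation independent of the event and reaching 10% to 40% by Week 104, exposure is 1,118 to 941 PY. The ratios are then 0.917 to 0.923 at 10 per 100 PY and 0.478 to 0.504 at 100 per 100 PY.

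**5. Dependence on exposure length.** With equal exposure T, the total-exposure formula gives (1 − exp(−λT)) / T. At an assumed 50 per 100 PY this is 44.7 for T = 24 weeks and 31.7 for T = 104 weeks.

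**6. Where the formulas agree.** They coincide for deaths. They also coincide for onset after a subject's final dose, provided at-risk time is capped at the last dose, which the SAP does not state. They nearly coincide when the event ends treatment: with dosing stopped 2 weeks after onset, a simulation of the 690 subjects returned 9.97 for a true rate of 10. There is one exception in ALL UPA. An event with onset soon after the Week 104 dose, in a subject who later reinitiates, is followed by further exposure, so the denominators differ.

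**The case against.** The best defence is that the at-risk sentence is the operative definition, with explicit rules for subjects with and without an event. On that reading the parenthetical only shows the conversion from days to years, and a specific definition would normally prevail over a general restatement. This is plausible as a reading of intent. It is not what the words say: they specify whose days are summed, namely all treated subjects, and give no cut-off at the first event. They are also the formula from which a programmer would naturally code.

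A second point is that the error would be visible. Numerator and denominator are to be presented, so every EAIR row in a group would show the same patient-years as the EAER. That makes detection likely, but only after the tables exist.

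Three limits stand. The figures above describe main-study exposure, not either SAP safety population. All event rates are assumed. The SAP plans no formal comparison between its two safety populations, so the dependence on exposure length affects how a reader sets the two tables side by side, not a planned contrast.

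**Conclusion.** The concern holds. SAP 10.1 gives two incompatible denominators for one rate in consecutive sentences, and nothing elsewhere says which governs. The consequence is conditional on the second being programmed; in that case the direction is certain and the EAIR is understated.

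Under a constant rate, with subjects staying on drug and planned main-study exposure, the understatement is about 2% at 2 per 100 PY, 8% at 10, 22% at 30 and just over half at 100. It is therefore negligible for rare AESIs and material for frequent categories such as any treatment-emergent adverse event. Early discontinuation barely changes this. Reinitiation and extension exposure are left out because the documents do not give them.

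The EAER is not affected. SAP Section 13.0 plans no formal testing, so neither type I error nor power is at issue. The text should be corrected before the safety tables are programmed.

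**What to change.** Keep the at-risk definition in SAP 10.1 and replace the parenthetical in the following sentence with: *calculated as total number of days at risk (exposure to first event for subjects with the event, total exposure for subjects without it) divided by 365.25*.

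The cost is one parenthetical in the SAP, with no new data and no new analysis.
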